5.2. Exclusion Criteria

Participants are excluded from the study if any of the following criteria apply:

1. Upper respiratory illness within the last 2 weeks
2. History of severe epistaxis
3. Allergic sensitivity to silicone or any other component of device
4. Sinonasal surgery in the last 3 months
5. Topical decongestant use in the last week
6. Nasal polyposis, purulence/edema, or other signs of sinusitis on exam
7. Sinusitis on imaging
8. Nasal crusting or ulceration on exam
9. Inability to read or understand English

5.3. Screen Failures

A screen failure occurs when a participant who has consented to participate in the clinical study is not subsequently assigned to study intervention/entered in the study. A minimal set of screen failure information is required to ensure transparent reporting of screen failure participants to meet the CONSORT publishing requirements and to respond to queries from regulatory authorities. Minimal information includes demography, screen failure details, eligibility criteria, and any SAE.

Individuals who do not meet the criteria for participation in this study (screen failure) may not be rescreened.

6. Study Intervention(s) and Concomitant Therapy

Study interventions are all pre-specified, investigational devices intended to be administered to the study participants during the study conduct.

6.1. Study Intervention(s) Administered

Table 1. Study Intervention(s) Administered

Intervention Label	Active	Sham
Intervention Name	SinuSonic device	Sham SinuSonic device
Intervention Description	The SinuSonic consists of a fully-disposable medical grade silicone nosepiece mounted to a resin body. The device is equipped with a flutter valve located at the top of the device which creates gentle, self-guided oscillating expiratory resistance. It provides administration of acoustic vibration at 128Hz and oscillating positive expiratory pressure.	Sham device with similar appearance that lacks positive end expiratory pressure and emits noise at non-therapeutic frequency.
Type	Active Device	Sham device
Dose Formulation	Other	Other
Unit Dose Strength(s)	2 minutes of device use	2 minutes of device use
Dosage Level(s)	Sinusonic device for 2 minutes, twice daily for 8 weeks	sham device for 2 minutes, twice daily for 8 weeks
Route of Administration	Other	Other
Use	experimental	sham comparator
IMP and NIMP/AxMP.	NIMP	NIMP
Sourcing	Acquired from the Healthy Humming LLC, Columbia, SC by the study PI	Acquired from the Healthy Humming LLC, Columbia, SC by the study PI
Packaging and Labeling	Device for study intervention will be provided in cardboard box. The active and sham device will be labelled identically and will include instructions on use and storage.	Sham device will be provided in a cardboard box. The active and sham device will be labelled identically and will include instructions on use and storage.

Table 2. Study Arm(s)

Arm Title	Arm 1	Arm 2
Arm Type	Active device	Sham comparator
Arm Description	Sinusonic device for 2 minutes, twice daily for 8 weeks	sham device for 2 minutes, twice daily for 8 weeks
Associated Intervention Labels	Not applicable	No applicable

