Just as efficacy for triptans was first demonstrated and popularized in the primary headache literature before utilization in sinus headache studies, medical devices are following a similar trend with the recent advent of transcutaneous stimulation devices.⁹ Recently, two studies investigating use of acoustic vibration with oscillating expiratory pressure applied to the nasal cavity for treatment of nasal congestion were performed looking at cohorts of patients with complaint of congestion.^{10,11} One study demonstrated a significant improvement in objective measures of nasal obstruction and both demonstrated improvements in subjective measures of obstruction. Of note, in both studies, investigators noted improvements in facial pain/pressure.

We recently conducted an open label trial to determine if simultaneous administration of acoustic vibration and oscillating expiratory pressure (using Sinusonic device) affects the severity of facial pain among patients with complaint of sinus headache. Twenty-nine patients (mean age 49 years, 55% female) completed our preliminary study without any major adverse events. At 4-weeks follow-up, facial pain visual analog scale (VAS) improved from mean standard deviation(SD) of 59.6+/-15.7 to 34.6+/-21.7(p<0.001) and approximately 70% of patients achieving a minimal clinically important difference (MCID) across all metrics. Eighty-six percent of subjects would use device again and recommend it to others. As the next step, we propose a randomized controlled trial. Preliminary data demonstrates that the device is low-risk, with high patient satisfaction, and patients are able to perform the intervention at home with ease.

In regards to device use, the device comes with a clear plastic tab at the base of the device. This tab must be removed prior to device use. For a full session, there is a trigger that must be held down after which

subjects should breathe in and out through their nose with a normal amount of force and speed. A gentle humming will be felt and heard and during exhalations, a fluttering sound will be appreciated. After a full session of use (2 minutes), the device will go into a rest mode for 6 minutes.

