2.2. Background

The SinuSonic device utilizes acoustic vibration with oscillating expiratory pressure and was first studied for the indication of nasal obstruction. A previous study of acoustic vibrations with oscitating expiratory pressure found significant improvements in objective and subjective metrics of nasal congestion/obstruction suggesting that physiologic changes may occur within the nasal cavity in response to device use. There have been two studies from separate institutions investigating use of acoustic vibrations on nasal congestion and interestingly patients noted improvement in secondary symptoms of facial pain and pressure. Although these study were focused on patients with nasal congestion, subjects improvements in facial pressure was an interesting finding. The question thus arose whether a device employing simultaneous acoustic vibrations and positive expiratory pressure to the nasal cavity could improve symptoms in patients with chief complaint of sinus headache. We recently conducted an open label trial to determine if simultaneous administration of acoustic vibration and oscillating expiratory pressure (using Sinusonic device) affects the severity of facial pain among patients with complaint of sinus headache. Twenty-nine patients (mean age 49 years, 55% female) completed our preliminary study without any major adverse events. At the 4-week follow-up, facial pain visual analog scale (VAS) improved from mean standard deviation(SD) of 59.6+-15.7 to 34.6+-21.7(p<0.001) and approximately 70% of patients achieving a minimal clinically important difference (MCID) across all facial pain metrics. Eighty-six percent of subjects would use device again and recommend it to others. As the next step, we propose a randomized controlled trial. Preliminary data demonstrates that the device is low-risk, with high patient satisfaction, and patients are able to perform the intervention at home with ease.

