4.1. Overall Design

- This is a parallel, two-arm, sham placebo controlled multicenter (Mayo AZ, Mayo FL and Mayo RST), clinical trial investigating use of the novel SinuSonic Device for sinus headache.
- The control group will be a sham device of similar appearance to the investigational device
- Participants will be healthy volunteers with complaint of sinus headache lacking objective evidence of sinonasal inflammation on exam or endoscopy
- Primary outcome measures of facial pain measured using facial pain VAS and BPI-SF will be assessed at baseline, Day 1, 2 week, 4 week, 6 week, and 8 weeks.
- Participants will be randomized in a 1:1 fashion; SinuSonic arm: Sham device, respectively.
- Total Duration of study participation will be 11 weeks; 2-3 weeks for screening and randomization and 8 weeks for the intervention component.

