6.1.1. Medical Devices

1. The Healthy Humming LLC manufactured medical devices (SinuSonic and sham device) will be provided for use in this study.
2. Instructions for medical device use are provided **in document “Healthy Humming Instructional Booklet”**
3. All device deficiencies (including malfunction, use error and inadequate labelling) shall be documented and reported by the investigator throughout the clinical investigation

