6.7. Continued Access to Study Intervention after the End of the Study

There will be no provision to provide continued access to study intervention after the end of the study. However, the active study intervention (sinusonic device) is available for purchase commercially.

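### Earlier users of the SinuSonic device are not excluded, although the sham is matched on appearance and labelling only, so they could recognise their arm and bias self-reported pain.

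*Combined protocol and SAP*

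**What the plan says.** The sham is described twice. Section 4.1 says: "The control group will be a sham device of similar appearance to the investigational device". Section 6.1 repeats the similar appearance and says that the sham "lacks positive end expiratory pressure and emits noise at non-therapeutic frequency". Section 6.1 adds that the two devices carry identical labels. Section 6.4 has an uninvolved third party dispense them and keeps investigators blinded.

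Of the active device, Section 6.1 says: "The device is equipped with a flutter valve located at the top of the device which creates gentle, self-guided oscillating expiratory resistance". The Introduction (Section 2) tells the reader what a session is like: "A gentle humming will be felt and heard and during exhalations, a fluttering sound will be appreciated".

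Section 1.1 states that participants are blinded. The primary endpoints are changes at 8 weeks in the facial pain VAS and the BPI-SF (Section 3), both rated by the participant (Section 7.1).

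On earlier exposure, Section 6.7 notes that "the active study intervention (sinusonic device) is available for purchase commercially", and Section 2.2 says: "We recently conducted an open label trial to determine if simultaneous administration of acoustic vibration and oscillating expiratory pressure". Twenty-nine patients completed that trial, and 86% said that they would use the device again and recommend it. None of the six criteria in Section 5.1 or the nine in Section 5.2 mentions earlier use. The Schedule of Activities and Section 8 contain no question on which arm participants believe they are in.

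**The concern.** The stated safeguards cover how the device looks, how it is labelled and who hands it out. None covers what the participant feels or hears during use. A newcomer has no reference for that. A person who has used the active device does: the resistance and the sound are both documented differences, and a sham without resistance could be recognised early in use.

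The people most likely to have this knowledge are also easy to reach. They have the complaint under study, and some took part in a trial run by the same team. If they recognise a sham, they may rate their pain as less improved; if they recognise the active device, as more improved. Both shifts favour the device. A larger sample would not remove them.

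**Working it through.** **The plan's own figure.** Section 8.4 claims over 90% power for 30% versus 70% response with 60 participants, 30 per arm, two-sided 5%. With unpooled variance, SE = √[(0.3×0.7 + 0.7×0.3)/30] = √0.014 = 0.1183, and 0.4/0.1183 − 1.96 = 1.42, which gives 92.2%. With pooled variance it is 89.3%. The claim reproduces, and this point does not affect it. The issue is bias, not precision.

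**What a participant could notice.**

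| Cue | Active | Sham | Source |
|---|---|---|---|
| Appearance | reference | similar | 4.1, 6.1 |
| Label | identical | identical | 6.1 |
| Expiratory resistance | present, made by the flutter valve | absent | 6.1 |
| Sound | 128 Hz; hum felt and heard | noise at a frequency called non-therapeutic | 6.1, 2 |
| Flutter on exhalation | heard | not stated | 6.1, 2 |

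Resistance and frequency differ by the protocol's own account. That the sham has no flutter is an inference: the flutter valve makes the resistance, and the sham has no positive expiratory pressure.

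**Who could use the cues.** In a parallel-group trial each participant handles one device. Only someone who has met the active device elsewhere can compare directly. Sections 2 and 6.7 show that such people exist, and Sections 5.1 and 5.2 let them in. No figure says how many would enrol.

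**How size would scale (illustration only; every bias input is assumed).** Suppose k of 30 sham participants recognise the sham and each reports d mm less improvement on the 0–100 mm VAS. The bias in the mean difference is then (k/30) × d.

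- One person: 10/30 = 0.33 mm at d = 10; 15/30 = 0.5 mm at d = 15.
- To reach 5 mm: k = 5×30/10 = 15 at d = 10; k = 5×30/15 = 10 at d = 15.

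Recognition in the active arm would add to this.

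To see what such a bias does to the false-positive rate, take the open-label SDs of 15.7 and 21.7 mm. The SD of change is √(15.7² + 21.7² − 2r×15.7×21.7), which is 26.8 mm at r = 0 and 15.5 mm at r = 0.7; r is assumed. Rounded to 27 and 16 mm, the SE of a difference between two independent arms is SD × √(2/30) = 6.97 or 4.13 mm. With no true effect, the two-sided 5% test rejects with probability Φ(b/SE − 1.96) + Φ(−b/SE − 1.96):

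| Bias b | SD 27 mm | SD 16 mm |
|---|---|---|
| 0 | 5% | 5% |
| 5 mm | 11% | 23% |
| 10 mm | 30% | 68% |

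At b = 0.5 mm and SD 16 mm, b/SE = 0.121 and the rate is 0.033 + 0.019 = 5.2%. One or two earlier users would hardly matter; many would.

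**The case against.** The strongest reply is that the sham is a reasonable one. It looks similar, makes noise, is labelled identically and is dispensed by a third party. Participants never hold both devices. The sham also still controls for natural history, regression to the mean and expectation among those who do not recognise it. All of this stands, and it rules out several stronger readings.

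- **That participants in general will recognise their arm.** The documents do not show this. A newcomer has no comparator, and no recognition rate is given.
- **That the protocol says the sham lacks the flutter users notice.** It does not. Section 6.1 mentions only pressure and frequency for the sham, and Section 2 speaks of hum and flutter, not of pressure.
- **That participants are told what to expect.** Section 6.1.1 says only "Instructions for medical device use are provided" in a named booklet. That booklet is not among the documents, and the Introduction is not shown to be text for participants.
- **That without arm guesses a positive result cannot be told apart from expectation.** This overstates what guesses offer. They measure blinding without repairing it, and even early guesses partly reflect whether the pain has eased.

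It is also fair to say that, if few earlier users would enrol, excluding them removes little bias. That is correct, but the cost is then equally small.

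**Conclusion.** The gap is real and narrow. The documents establish that the sham differs from the active device in resistance and sound, that the outcomes are self-reported, that earlier users exist in this indication, and that nothing keeps them out. They could recognise their arm and bias the VAS and BPI-SF in the device's favour.

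The documents do not establish how many would enrol, how many would recognise a sham, or by how much their ratings would shift. The millimetre and false-positive figures above show only how bias would scale under assumed inputs; they are not estimates for this trial. There is no contradiction or calculation error in the plan here. This is a low-cost improvement to eligibility and does not show that the blinding fails.

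**What to change.** Add a tenth criterion to Section 5.2: any previous use of the SinuSonic device, including participation in the earlier open-label trial. Ask about it at screening with the medical history. The cost is one question and the loss of some candidates. The loss is probably small, but the documents give no count.

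Two additions are optional and secondary:

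- Confirm that the participant instructions are identical in both arms and do not describe sensations that only one device produces. This costs a document check.
- Add one arm-guess item, with the reason for the guess, at an early questionnaire point such as Week 2 in the Schedule of Activities. Report it by arm, descriptively. It would show how well blinding held but should not be used to adjust the treatment effect.

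No new sham, larger sample or change of endpoint is needed. For newcomers the sensory difference between the devices remains.

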6.1.1. Medical Devices

1. The Healthy Humming LLC manufactured medical devices (SinuSonic and sham device) will be provided for use in this study.
2. Instructions for medical device use are provided **in document “Healthy Humming Instructional Booklet”**
3. All device deficiencies (including malfunction, use error and inadequate labelling) shall be documented and reported by the investigator throughout the clinical investigation

6.2. Preparation, Handling, Storage, and Accountability

4. Only participants enrolled in the study may receive study intervention, and participants themselves may administer study intervention.
5. The investigator is responsible for study intervention accountability, reconciliation, and record maintenance (i.e., receipt, reconciliation, and final disposition records).

6.3. Assignment to Study Intervention

On Day 0 (baseline), participants will be assigned a unique number (Subject ID) in ascending numerical order at each study site. The randomization will be implemented in the EDC system, according to the randomization schedule generated prior to the study by the statistics department at Mayo Clinic. Each participant will be dispensed blinded study intervention .

6.4. Blinding, Masking

Participants will be randomly assigned in a 1:1 ratio to receive study intervention. Investigators will remain blinded to each participant's assigned study intervention throughout the course of the study. To maintain this blind, an otherwise uninvolved third party will be responsible for the reconstitution and dispensation of all study intervention and will endeavor to ensure that there are no differences in time taken to dispense following randomization.

Sponsor safety staff may unblind the intervention assignment for any participant with an SAE. If the SAE requires that an expedited regulatory report be sent to one or more regulatory agencies, a copy of the report, identifying the participant's intervention assignment, may be sent to investigators in accordance with local regulations and/or sponsor policy.

6.5. Study Intervention Compliance

Participant will self-administer the medical intervention and compliance with study intervention will be assessed at each visit. Compliance will be assessed by direct questioning during the study visits, where participants will be asked to report the number of days in past two weeks that they used the study intervention and documented in the source documents and relevant form. The adherence to the prescribed dosage regimen should be recorded.

Intervention start and stop dates, including dates for intervention delays and/or dose reductions will also be recorded.

6.6. Dose Modification

Any dose modification, including the duration and frequency of administration of sinusonic/sham device will not be permitted.

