2.3. Benefit/Risk Assessment

Based on available clinical studies, application of acoustic vibration with positive end expiratory pressure to the nasal cavity is a relatively low-risk intervention. In two separate studies investigating its use for nasal congestion, no adverse events were reported in 90 subjects. In a more recent study looking specifically at patients with sinus headache, one patient noted mild epistaxis that resolved following use.

Similarly, four patients noted some mild-moderate discomfort during device use. No permanent or major adverse events were noted.

More detailed information about the known and expected benefits and risks and reasonably expected adverse events (AEs) of SinuSonic device may be found in the package insert and summary of product characteristics.

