2.3.3. Overall Benefit Risk Conclusion

Taking into account the measures taken to minimize risk to participants participating in this study, the potential risks identified in association with the SinuSonic device are justified by the anticipated benefits that may be afforded to participants with Sinus headache.

3. Objectives, Endpoints, and Estimands

Objectives	Endpoints
Primary	

 To determine superiority of SinuSonic intervention versus control in treatment of facial pain for patients with complaint of sinus headache that lack objective evidence of sinonasal inflammation 	
 Change in facial pain visual analogue scale at 8 weeks Change in Brief Pain Inventory Short Form at 8 weeks
Secondary	

 To determine safety of device use 	
 Number and percent of subjects reporting pain with device use Number and percent of subjects reporting epistaxis Change in Nasal Obstruction Symptom Evaluation (NOSE) Score at 8 weeks
Tertiary	

 To determine device use satisfaction 	
 Number and percent of subjects that would use the device again Number and percent of subjects that would recommend the device to others

Primary estimand

The primary clinical question of interest is:

What is the improvement in facial pain measured by facial pain VAS, and BPI-SF in patients with sinus headache treated with SinuSonic device versus a sham device regardless of discontinuation of investigational intervention for any reason and regardless of initiation of rescue medication or change in background medication.

The estimand is described by the following attributes:

- Population: Patients with complaint of sinus headache lacking objective evidence of sinonasal inflammation of nasal endoscopy or imaging
- Endpoint: change from baseline to 8 weeks in facial pain VAS, and BPI-SF
- Treatment condition:

the investigational interventions regardless of discontinuation for any reason, with or without rescue medication or change in background medication (treatment policy strategy).

- Remaining intercurrent events:

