4.3. Justification for Dose

For this device, the term *dose* refers to the number of 3-minute treatment sessions.

Justification for device use is based on manufacturer's recommendation and efficacy with use in prior studies. The device will be turned on and silicone nasal mask placed over the nose and participants will breathe similar to their baseline nasal breathing against the device for 2 doses (two 3-minute treatment session). The device will be used twice daily, any the protocol will not allow any deviations in treatment.

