6.9. Discontinuation of Study Intervention

In rare instances, it may be necessary for a participant to permanently discontinue study intervention. If study intervention is permanently discontinued, the participant should, if at all possible, remain in the study to be evaluated for 1 week. See the SoA for data to be collected at the time of discontinuation of study intervention and follow-up and for any further evaluations that need to be completed.

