6.10. Participant Discontinuation/Withdrawal from the Study

- A participant may withdraw from the study at any time at the participant's own request for any reason (or without providing any reason).
- A participant may be withdrawn at any time at the discretion of the investigator for safety, behavioral, or compliance reasons.
- At the time of discontinuing from the study, if possible, an early discontinuation visit should be conducted, as shown in the SoA. See SoA for data to be collected at the time of study discontinuation and follow-up and for any further evaluations that need to be completed.
- The participant will be permanently discontinued from the study intervention and the study at that time.
- If the participant withdraws consent for disclosure of future information, the sponsor may retain and continue to use any data collected before such a withdrawal of consent.
- If a participant withdraws from the study, the participant may request destruction of any samples taken and not tested, and the investigator must document this in the site study records.

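### Section 6.10 lets an investigator end a participant's outcome collection for poor compliance, although the treatment-policy estimand needs that participant's Week-8 value

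*Combined protocol and SAP*

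**What the plan says.** **Regimen.** Section 4.3 states that "the protocol will not allow any deviations in treatment", and Section 6.6 adds: "Any dose modification, including the duration and frequency of administration of sinusonic/sham device will not be permitted". Section 6.5 has sites ask participants about their use and adds: "Intervention start and stop dates, including dates for intervention delays and/or dose reductions will also be recorded".

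**Withdrawal by the investigator.** Section 6.10 makes compliance one of three grounds on which the investigator may withdraw someone. It does not define compliance or set a threshold. The consequence is stated without exception: "The participant will be permanently discontinued from the study intervention and the study at that time". An early discontinuation visit is requested where possible.

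**Stopping the device only.** This is handled separately in Section 6.9: "the participant should, if at all possible, remain in the study to be evaluated for 1 week".

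**Estimand.** Section 3 gives the primary treatment condition as "the investigational interventions regardless of discontinuation for any reason, with or without rescue medication or change in background medication (treatment policy strategy"). The endpoint is the change from baseline to 8 weeks in facial pain VAS and BPI-SF, summarised as a difference in mean changes.

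**Analysis.** Section 8.2 analyses efficacy in all randomized participants, by planned intervention. Sections 8.3.1 and 8.3.1.1 drop missing values and name no imputation or model for them.

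**The concern.** Compliance is observed after randomization and may itself depend on the assigned device. Section 6.1 describes a sham without expiratory pressure, so tolerability may differ between arms. Users of either device who feel no benefit may also lapse. If low use leads to withdrawal, and low use is related to arm and to pain, the participants who still have Week-8 values are no longer the groups that were randomized.

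This route differs from the one in Section 6.9. There, a participant stops the device and is followed for a week. Here, a participant may still be using the device in part and be willing to answer questionnaires, and it is the investigator who ends data collection. Repairing Section 6.9 alone would leave this route open. With no threshold in Section 6.10, the three sites named in Section 4.1 could also apply it differently.

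**Working it through.** **1. Follow one participant through the plan.** Someone uses the device well below the fixed regimen.
- Under 6.5 the reduced use is recorded.
- Under 6.10 the investigator may withdraw the participant for compliance. Device use and study participation then both end, so no Week-8 VAS or BPI-SF follows.
- Under 8.2 the participant stays in the full analysis set by name. Under 8.3.1 and 8.3.1.1 the absent Week-8 change is left out, with nothing in its place.
- Under Section 3 that change belongs in the estimate.

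**2. Reproduce the plan's power.** Inputs from Section 8.4: 30% versus 70% response, N = 60, two-sided 5%. Allocation is 1:1 (Section 6.4), so n = 30 per arm.

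Pooled normal approximation: power = Φ[(|p1 − p2| − 1.96·√(2·p̄(1 − p̄)/n)) / √((p1(1 − p1) + p2(1 − p2))/n)], with p̄ = 0.5.

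n = 30: (0.40 − 1.96 × 0.1291)/0.1183 = 1.242, so power is 89.3%. The unpooled version gives 0.40/0.1183 − 1.96 = 1.421, or 92.2%, which matches the stated figure of over 90%.

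**3. Balanced loss unrelated to outcome.** The documents give no withdrawal rate, so these rates are assumptions.

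| Loss per arm | n per arm | Power, pooled | Power, unpooled |
|---|---|---|---|
| 0% | 30 | 89.3% | 92.2% |
| 10% | 27 | 85.7% | 89.4% |
| 20% | 24 | 81.2% | 85.6% |
| 30% | 21 | 75.5% | 80.7% |

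The Synopsis caps enrolment at 60, and no dropout allowance is stated. This uses the plan's responder basis for sizing; the estimand is a difference in means, for which no power is given.

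**4. Loss related to arm and outcome: an extreme case.** Assume true response is 30% in both arms (9 of 30) and that withdrawals occur in one arm only, all of them non-responders. Observed response in that arm is 9/(30 − number withdrawn).

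| Withdrawn from one arm | Observed response | Apparent difference | Rejection rate at nominal 5% |
|---|---|---|---|
| 3 (10%) | 9/27 = 33.3% | 3.3 points | 5.9% |
| 6 (20%) | 9/24 = 37.5% | 7.5 points | 9.0% |
| 9 (30%) | 9/21 = 42.9% | 12.9 points | 15.8% |

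For the 20% row: p̄ = 18/54 = 0.333, the null standard error is 0.1291 and the actual one is 0.1295. Then Φ[(0.075 − 0.2530)/0.1295] + Φ[(−0.075 − 0.2530)/0.1295] = 0.085 + 0.006 ≈ 0.090.

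If the active arm loses the non-responders, the spurious difference favours the device. If the sham arm loses them, the same figures apply against it. The table shows how large the effect could become, not what to expect.

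**The case against.** The strongest reply is that the route is only a possibility. Section 6.10 says the investigator may withdraw a participant, and no text ties a missed or shortened session to removal. Section 6.4 keeps investigators blinded, which limits deliberate selection by arm. Section 6.10 asks for an early discontinuation visit, and Section 8.2 keeps everyone randomized in the analysis set. The lost data also overlap with those lost through Section 6.9, and one repair could serve both.

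Much of this stands, and it limits how strongly the point can be put. None of it restores a Week-8 value. A visit at the time of withdrawal is not a Week-8 assessment, and in the available text of the Schedule of Activities the early discontinuation column shows no mark for VAS or BPI-SF. Blinding does not prevent withdrawals that follow use when use differs by arm, and the Synopsis describes the study as blinded to participants only.

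A reader might infer three stronger things that the documents do not support:
- **That 6.5 and 6.6 contradict each other.** Forbidding changes to a regimen and recording departures from it are compatible. Section 6.6 also contains no removal rule.
- **That about 17% of the active arm would be lost.** Section 2.3 reports one mild epistaxis and says "Similarly, four patients noted some mild-moderate discomfort during device use"; at most 5/29 = 17% if these were different people among the 29 completers. Section 2.3 gives no denominator, these are event counts rather than withdrawals, and anyone counted among the 29 finished that study. They cannot be turned into a withdrawal rate or a bias in millimetres.
- **That the bias favours the device.** No compliance data by arm are given, and removing poor responders from the sham arm would work against the device.

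**Conclusion.** The concern holds in a limited form. Section 6.10 permits outcome collection to end because of compliance, and the missing-data rule then removes that participant from a Week-8 comparison in which the estimand includes them. This follows from the text alone.

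The size and direction of any bias cannot be determined from the documents. If loss is balanced and unrelated to outcome, only power suffers: about 8 points at an assumed 20% per arm (89.3% to 81.2%, pooled). If loss is related to both arm and outcome, the contrast can move either way; the one-arm case in the working marks an extreme. If investigators never use the compliance ground, nothing is lost. The point deserves correction because the mismatch is plain and cheap to remove, not because harm has been shown.

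**What to change.** Reconcile the estimand in Section 3 with Sections 6.9, 6.10, 8.3.1 and 8.3.1.1, so that the protocol:
- separates stopping or under-using the device from leaving the study;
- states that non-compliance alone does not end outcome collection;
- keeps sending off-regimen participants every remaining questionnaire in the Schedule of Activities through Week 8, unless they withdraw consent;
- includes those values in the full-analysis-set comparison.

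As a minor clarification, Sections 4.3, 6.5 and 6.6 should say that recorded delays and reductions are deviations from the fixed regimen, if that is what is meant. Any rule on device use itself is for the sponsor to set.

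The cost is amendment wording: the questionnaires are remote and the Week-8 assessment is already scheduled. The small downside is that data from poorly adherent participants stay in the analysis, as the stated estimand intends.
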